5.3.1 Dose Modification for Adverse Events

The following guidance is for dose modification of CX-072 and/or ipilimumab (ie, study treatment). Delays or permanent discontinuation of study treatment may be required as outlined in [Table 5](#) and [Section 5.3.2](#). Dose reduction of any study treatment is not permitted. Guidance is adapted from American Society of Clinical Oncology Clinical Practice Guidelines ([Brahmer 2018](#)), which should be referenced for additional detail and information when assessing and managing AEs that are considered to be potentially immune related.

Additional recommendations for interventions of irAEs depending on severity of the event are provided in [Section 5.3.3](#).

Table 5 Dose Modifications for Select Adverse Events

Adverse Event	Grade 1	Grade 2	Grade 3	Grade 4
Skin toxicities including dermatitis, Stevens-Johnson syndrome, or toxic epidermal necrolysis See also Section 5.3.3.11	No action; G1 does not apply to severe cutaneous toxicities (eg, Stevens-Johnson syndrome, toxic epidermal necrolysis).	Hold until recovery to \leq G1 or baseline.	Hold until recovery to \leq G1 or baseline. Consult with a dermatologist.	Permanently discontinue study treatment.
Colitis ^a See also Section 5.3.3.1	No action; may consider holding study treatment and resuming if toxicity does not exceed G1	Hold until recovery to \leq G1. Consider permanent discontinuation of ipilimumab. ^b	Hold until recovery to \leq G1. Consider permanent discontinuation of ipilimumab. ^b	Permanently discontinue study treatment.
Increased serum transaminases (AST/ALT) or total bilirubin See also Section 5.3.3.2	No action; monitor laboratory values 1 to 2 times per week.	Hold until recovery to \leq G1 or baseline on prednisone \leq 10 mg per day.	Permanently discontinue study treatment.	Permanently discontinue study treatment.
Pneumonitis See also Section 5.3.3.3	No action	Hold until recovery to \leq G1.	Permanently discontinue study treatment	Permanently discontinue study treatment.
Hypothyroidism or hyperthyroidism See also Section 5.3.3.4	No action	Hold until recovery to \leq G1 or baseline.	Hold until recovery to \leq G1 or baseline (with hormone replacement for hypothyroidism).	Permanently discontinue study treatment.
Adrenal insufficiency See also Section 5.3.3.6	Consider holding until subject is stabilized.	Hold until recovery to \leq G1 or baseline with hormone replacement.	Hold until recovery to \leq G1 or baseline with hormone replacement.	Hold until recovery to \leq G1 or baseline with hormone replacement
Hypophysitis See also Section 5.3.3.8	Consider holding study treatment until stabilized on replacement therapy.	Hold until recovery to \leq G1 or baseline with hormone replacement.	Hold until recovery to \leq G1 or baseline with hormone replacement.	Hold until recovery to \leq G1 or baseline with hormone replacement
Type 1 diabetes See also Section 5.3.3.7	NA; G1 does not apply to subjects with evidence of Type 1 diabetes or ketosis.	Hold until recovery to \leq G1 or baseline. Urgent endocrine consultation for all subjects. Initiate insulin therapy for all subjects.	Hold until recovery to \leq G1 or baseline. Urgent endocrine consultation for all subjects. Initiate insulin therapy for all subjects.	Hold until recovery to \leq G1 or baseline. Urgent endocrine consultation for all subjects. Initiate insulin therapy for all subjects.

Table 5 Dose Modifications for Select Adverse Events (continued)

Adverse Event	Grade 1	Grade 2	Grade 3	Grade 4
Creatinine See also Section 5.3.3.5	No action; consider holding treatment pending work-up.	Hold until recovery to ≤G1 or baseline. Consult nephrology.	Hold until recovery to ≤G1 or baseline. Permanently discontinue for Grade 3 nephritis.	Permanently discontinue study treatment.
Pancreatitis See also Section 5.3.3.10	Monitor for symptoms and laboratory abnormalities.	Hold until recovery to ≤G1 or baseline.	Hold until recovery to ≤G1 or baseline.	Permanently discontinue study treatment.
Myocarditis See also Section 5.3.3.5	NA	For any clinical suspicion, refer to cardiologist for workup, diagnosis, and treatment. Hold study treatment and contact Sponsor Medical Monitor to discuss discontinuation of study.		
Encephalitis or meningoencephalitis See also Section 5.3.3.10		For any clinical suspicion, refer to neurologist for workup, diagnosis, and treatment. Hold study treatment and contact Sponsor Medical Monitor to discuss discontinuation of study treatment.		
Ocular inflammatory toxicity (eg, uveitis, conjunctivitis, orbital inflammation, episcleritis) See also Section 5.3.3.9	Refer to ophthalmology.	Hold until recovery to ≤G1 or baseline. Refer to ophthalmology.	Permanently discontinue study treatment. Refer to ophthalmology.	Permanently discontinue study treatment. Refer to ophthalmology.
Guillain-Barré syndrome or myasthenia gravis		For any clinical suspicion, refer to neurologist for workup, diagnosis, and treatment. Hold study treatment and contact Sponsor Medical Monitor to discuss discontinuation of study treatment. For any confirmed diagnosis of any grade, treatment must be discontinued.		
Other immune-related adverse reactions (except those listed above) See also Section 5.3.3.12	No action	No action; consider holding treatment depending on organs involved.	Hold and contact Sponsor Medical Monitor to discuss treatment, which may include administration of systemic steroids.	Hold and contact Sponsor Medical Monitor to discuss treatment, which may include administration of systemic steroids.
Grade 3 adverse reactions (except those listed above)	NA	NA	Hold until recovery to ≤G1 or baseline.	NA
Life-threatening or Grade 4 adverse reactions (except those listed above)	NA	NA	NA	Permanently discontinue study treatment.

^a Based on CTCAE for diarrhea as most often used clinically.

^b After consultation with Sponsor Medical Monitor.

ALT = alanine aminotransferase; AST = aspartate aminotransferase; CTCAE = Common Terminology Criteria for Adverse Events; G1 = Grade 1; NA = not applicable; PD-L1 = programmed death ligand 1.

Delays in CX-072 treatment will also result in a delay of ipilimumab.

Resume study treatment in subjects whose adverse reactions recover to Grade ≤ 1 or baseline, at the discretion of the Investigator unless otherwise stated in [Table 5](#) and/or [Section 5.3.3.12](#).

Refer to the current local package insert for ipilimumab for common adverse reactions, black box warnings, dose modification, and other information pertaining to the management of AEs associated with ipilimumab treatment.

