5.3.3.1 Immune-related Colitis

Counsel subject to inform the Investigator of any abdominal pain, nausea, cramping, blood or mucus in stool or changes in bowel habits, fever, abdominal distention, obstipation, or constipation.

For Grade 1 events, consider temporary withholding of treatment to confirm toxicity does not exceed Grade 1. Withhold study treatment for Grade 2 or 3 immune-related colitis. For moderate

(Grade 2) colitis administer corticosteroids, unless diarrhea is transient, starting with initial dose of 1 mg/kg per day prednisone or equivalent. Gastroenterology should be consulted and should consider permanent discontinuation of ipilimumab. For severe (Grade 3) or life-threatening (Grade 4) colitis, administer corticosteroids at a dose of 1 to 2 mg/kg per day prednisone equivalents (for Grade 3) or 1.0 to 2 mg/kg per day methylprednisolone equivalents (for Grade 4) followed by corticosteroid taper. If Grade 3 symptoms persist for ≥ 3 to 5 days or recur after improvement, consider administering IV corticosteroid or noncorticosteroid (eg, infliximab). Consider colonoscopy/GI endoscopy in cases where subjects have been on immunosuppression and may be at risk for opportunistic infections as an independent cause for diarrhea (ie, CMV colitis) and for those who are anti-TNF or corticosteroid refractory. When symptoms improve to \leq Grade 1, taper corticosteroids over at least 4 to 6 weeks before resuming treatment, although resuming treatment while on low-dose corticosteroid may also be an option after an evaluation of the risks and benefits. Permanently discontinue treatment for Grade 4 or recurrent colitis upon restarting study treatment.

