5.3.3.3 Immune-related Pneumonitis

Monitor subjects for signs and symptoms of pneumonitis. Subjects with Grade 1 pneumonitis should be monitored weekly and treatment should be held if there is radiographic evidence of pneumonitis progression. Treatment may be resumed with radiographic evidence of improvement or resolution. If no improvement, should treat as Grade 2. Subjects should be monitored weekly. For Grade 2 pneumonitis, recommend treatment with corticosteroids at a dose of 1 to 2 mg/kg per day prednisone equivalents, followed by a corticosteroid taper by 5 to 10 mg per week over 4 to 6 weeks. Consider bronchoscopy with bronchoalveolar lavage and empirical antibiotics. Monitor every 3 days. If no improvement after 48 to 72 hours of prednisone, treat as Grade 3. For Grade 3 pneumonitis, empirical antibiotics and corticosteroids (prednisolone IV 1 to 2 mg/kg per day) should be administered. If no improvement after 48 hours, may add 5 mg/kg infliximab or mycophenolate mofetil IV 1 g twice a day or IV immunoglobulin for 5 days or cyclophosphamide; taper corticosteroids over 4 to 6 weeks. Pulmonary and infectious disease consults should be sought if necessary. Subjects should be hospitalized for further management.

Withhold study treatment for Grade 2 immune-related pneumonitis and permanently discontinue treatment for Grade 3 or 4 or recurrent pneumonitis upon restarting study treatment.

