5.3.3.5 Immune-related Myocarditis

Monitor subjects for myocarditis prior to and periodically during treatment. For all grades of myocarditis, permanent treatment discontinuation should be discussed. Cardiology should be consulted, and high dose corticosteroids should be administered (1 to 2 mg/kg of prednisone initiated rapidly (oral or IV depending on symptoms). In subjects without an immediate response to high-dose corticosteroids, consider cardiac transplant rejection doses of corticosteroids (methylprednisolone 1 g every day) and the addition of either mycophenolate, infliximab, or anti-thymocyte globulin. Permanently discontinue for any >Grade 2 myocarditis.

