5.3.3.10 Immune-related Encephalitis or Meningoencephalitis

Monitor for changes in neurologic function. Withhold study treatment for new onset or moderate to severe neurologic symptoms and evaluate to rule out infectious or other causes of neurologic deterioration. Withhold study treatment for Grade 1, Grade 2, or Grade 3 events and consult with neurology. Consider concurrent IV acyclovir until polymerase chain reaction (PCR) results are obtained and negative, and treatment with methylprednisolone and additional treatment (eg, IV immunoglobulin, rituximab as recommended by neurology consultation). Permanently discontinue treatment for confirmed diagnosis of autoimmune encephalopathy.

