5.3.3.12 Other Immune-related Adverse Reactions

For any suspected immune-related adverse reactions, exclude other causes. Based on the severity of the adverse reaction, withhold study treatment, administer high-dose corticosteroids, and/or if appropriate, initiate hormone replacement therapy. Upon improvement to Grade ≤ 1 , initiate corticosteroid taper and continue to taper over at least 1 month. Consider restarting study treatment after completion of corticosteroid taper based on the severity of the event.

Refinement of the recommended treatment of TRAEs will be made as the study progresses.

If any of the immune-related symptoms worsen or do not improve with the guidelines above, tumor necrosis factor alpha (TNF α) inhibitors may be administered at the discretion of the Investigator.

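### The resume sentence below Table 5 does not except the recurrence stops for colitis and pneumonitis in Section 5.3.3, and Table 5 shows two other mandatory stops only as hold-and-discuss

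*Combined protocol and SAP*

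**What the plan says.** Section 5.3.1 of the Module (the combined protocol and SAP) puts the holding and stopping rules by event and grade in Table 5. A sentence below the table lets treatment resume once a reaction has recovered to Grade 1 or lower "or baseline, at the discretion of the Investigator unless otherwise stated in" Table 5 and/or Section 5.3.3.12. Section 5.3.3.12 covers other immune-related reactions and sets no permanent stop. On restart it says: "Consider restarting study treatment after completion of corticosteroid taper based on the severity of the event".

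Four other subsections of 5.3.3 do set stops that matter here:

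- Colitis (5.3.3.1): "Permanently discontinue treatment for Grade 4 or recurrent colitis upon restarting study treatment".
- Pneumonitis (5.3.3.3): "permanently discontinue treatment for Grade 3 or 4 or recurrent pneumonitis upon restarting study treatment".
- Myocarditis (5.3.3.5): "Permanently discontinue for any >Grade 2 myocarditis". The same subsection also says "For all grades of myocarditis, permanent treatment discontinuation should be discussed".
- Encephalitis (5.3.3.10): "Permanently discontinue treatment for confirmed diagnosis of autoimmune encephalopathy".

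In Table 5, Colitis Grades 2 and 3 and Pneumonitis Grade 2 call for a hold until recovery and do not mention recurrence. The two colitis cells add only "Consider permanent discontinuation of ipilimumab", after consultation with the Medical Monitor (footnote b). The myocarditis and encephalitis rows require specialist referral, a hold, and contact with the Medical Monitor to discuss discontinuation.

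**The concern.** A resume rule with a closed list of exceptions should name every place where a stop is written. This one names Table 5 and a single subsection of 5.3.3, and that subsection has no stop. Someone working from Table 5 and the sentence beneath it could take a second episode of Grade 2 or 3 colitis, or of Grade 2 pneumonitis, as one more hold followed by a discretionary restart. Sections 5.3.3.1 and 5.3.3.3 end treatment at that point. Section 5.3.1 does not allow dose reduction, so any restart is at the full dose of the drug given. For myocarditis above Grade 2 and confirmed autoimmune encephalopathy, a mandatory stop can look like a matter for discussion.

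What is at stake is subject safety and uniform handling across about 40 sites. Colitis is a foreseeable event: one of the two dose-limiting toxicities at the dose level above the combination MTD was Grade 3 colitis (Section 1.3.2), and Part A doses at the equivalent of the MTD (Section 1.5).

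**Working it through.** No sample size, power or error rate is involved. The check sets each permanent stop in 5.3.3 beside the matching Table 5 row.

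**Step 1. Subsections with a permanent stop.** There are 12 subsections (5.3.3.1 to 5.3.3.12). Five set no permanent stop: 5.3.3.6, 5.3.3.7, 5.3.3.8, 5.3.3.11 and 5.3.3.12. That leaves 12 − 5 = 7.

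**Step 2. Comparison with Table 5.**

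| Subsection | Permanent stop in 5.3.3 | Table 5 |
|---|---|---|
| 5.3.3.1 Colitis | Grade 4; recurrent | Grade 4 only |
| 5.3.3.2 Hepatitis | Grades 3, 4 | Same |
| 5.3.3.3 Pneumonitis | Grades 3, 4; recurrent | Grades 3, 4 only |
| 5.3.3.4 Thyroid | Grade 4 | Same |
| 5.3.3.5 Myocarditis | Above Grade 2 | Hold and discuss |
| 5.3.3.9 Ocular | Grades 3, 4 | Same |
| 5.3.3.10 Encephalitis | Confirmed autoimmune encephalopathy | Hold and discuss |

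Three of the seven are carried in full. The other 7 − 3 = 4 each lack one stop.

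**Step 3. Where the resume sentence conflicts with a stop.** A conflict needs a cell that holds until recovery, with nothing said on recurrence, and a recurrence stop in 5.3.3. There are two such cells for colitis (Grades 2 and 3) and one for pneumonitis (Grade 2): 2 + 1 = 3 cells in 2 rows. Colitis Grade 4 and Pneumonitis Grades 3 and 4 already stop treatment at first occurrence. Section 5.3.3 gives no grade for a recurrence. If a Grade 1 recurrence counts, the two Grade 1 cells join and the total is 3 + 2 = 5.

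**Step 4. Where the stop is left open.** Myocarditis and encephalitis make 2 rows. The catch-all row for Grade 4 reactions does not fill the gap, because it excludes events already listed. By contrast, the Guillain-Barré/myasthenia gravis row has the same hold-and-discuss text and then adds a mandatory stop on confirmed diagnosis.

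**Step 5. Other routes to the stops.** Section 4.11 refers to 5.3.1. The opening of 5.3.1 locates permanent discontinuation in Table 5 and 5.3.2, and 5.3.2 refers to Table 5. The two stops that 5.3.2 adds concern steroid taper and failure to recover within 12 weeks, so neither covers a recurrence that resolves. Section 5.3.1 does send the reader to 5.3.3, but for supplementary recommendations. The pointers in the Table 5 rows reach all 7 of the 7 subsections with a stop.

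**Step 6. Precedence.** The Module has two precedence clauses: Module over Core on subject care (Section 1), and SAP over Module on analyses (Section 10.2). Neither ranks Table 5 against 5.3.3.

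**The case against.** The best reply is that an Investigator can obey every sentence at once. The resume sentence defers to Table 5 as well as to 5.3.3.12, and Table 5 points correctly to every subsection with a stop. No cell tells anyone to resume after a recurrence. The resume rule is general and discretionary, the recurrence stops are specific and mandatory, and the specific rule is normally applied. Section 4.11 also requires a stop when an adverse event precludes safe administration, qualifying immune-related events are recorded within 24 hours (Section 9.7), and a DSMB reviews safety.

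Much of this stands, and it limits the weight. It does not settle precedence: a pointer takes the reader to the other rule without saying which governs, and 5.3.1 presents 5.3.3 as recommendations. Section 4.11, the 24-hour recording and the DSMB are matters of judgement, reporting or oversight; none states the missing stops.

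Three stronger readings are tempting, and the documents do not support them:

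- A reader might infer that the plan leaves restart after myocarditis or encephalitis to the Investigator alone. Both rows require a hold and Medical Monitor contact, so the stop is left open and not overridden.
- A reader might infer that the stops are missing or cannot be reached from Table 5. They are written in 5.3.3, and the row pointers lead to them.
- A reader might infer an effect on objective or pathologic response. The documents give no rate for these events or for wrongful restarts, so no such effect can be derived.

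**Conclusion.** The inconsistency is real and of modest weight. The exception list in the resume sentence is wrong for an operative safety rule. It produces a conflict between a general permission and a specific stop in three Table 5 cells, or five if a Grade 1 recurrence counts. In two further rows a mandatory stop appears discretionary. No expected number of affected subjects can be given.

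The conclusion rests on the Module text alone. The Core, the ipilimumab prescribing information and the cited management guideline are not in the documents and may contain further stops or guidance. A reader might suppose that 5.3.3.12 was written where 5.3.3 was meant. That is plausible, but the documents do not say so, and the correction does not depend on it.

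**What to change.** 1. In the resume sentence, replace the reference to Section 5.3.3.12 with Section 5.3.2 and/or Section 5.3.3.
2. In Section 5.3.2, name Section 5.3.3 beside Table 5 as a source of permanent stops, and add: *where they differ on permanent discontinuation, the stricter rule applies*.
3. In the Colitis Grade 2 and Grade 3 cells, add a permanent stop for recurrent colitis on restart, citing 5.3.3.1. In the Pneumonitis Grade 2 cell, add the same for recurrent pneumonitis, citing 5.3.3.3. Have the sponsor state whether a Grade 1 recurrence counts, since the Grade 1 cells currently call for no action and an ungraded stop would contradict them. Keep the word colitis: footnote a grades that row on diarrhea, and the stop should not widen to any recurrent diarrhea.
4. Carry "Permanently discontinue for any >Grade 2 myocarditis" into the myocarditis row and "Permanently discontinue treatment for confirmed diagnosis of autoimmune encephalopathy" into the encephalitis row.
5. Optional: correct the Creatinine and Pancreatitis pointers, which lead to the myocarditis and encephalitis subsections.

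The cost is amendment wording: two sentences, four table rows, one sponsor decision on Grade 1 recurrence, and two optional cross-references. No visits or data are added, and each stop is already in Section 5.3.3.

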5.3.2 Study Treatment Discontinuation for Adverse Events

Permanent discontinuation of study treatment may be required as dictated in Table 5.

If CX-072 is discontinued, ipilimumab will also be discontinued.

If ipilimumab is discontinued, treatment with CX-072 may continue/resume after discussion and agreement between the Investigator and the Sponsor Medical Monitor that this would be in line with risk benefit for the individual subject.

Study treatment should be permanently discontinued for either of the following:

- Inability to reduce corticosteroid dose to ≤ 10 mg of prednisone or equivalent per day within 12 weeks of initiation of corticosteroid
- Persistent Grade 2 or 3 treatment-related adverse reactions that do not recover to Grade ≤ 1 or baseline or resolve within 12 weeks after the last dose of study treatment

For adverse reactions that do not recover within 12 weeks, the Investigator must contact the Sponsor Medical Monitor to determine if the subject should be permanently withdrawn from study treatment or if a longer period of waiting for resolution is warranted.

5.3.3 Management of Immune-related Toxicity

All AEs should be monitored and managed according to standard of care. Refer to “Management of Immune-related Adverse Events in Patients Treated with Immune Checkpoint Inhibitor Therapy: American Society of Clinical Oncology Clinical Practice Guideline” ([Brahmer 2018](#)) for specific guidance. For any suspected immune-related toxicities, other causes should be excluded and treated appropriately in accordance with standard of care.

5.3.3.1 Immune-related Colitis

Counsel subject to inform the Investigator of any abdominal pain, nausea, cramping, blood or mucus in stool or changes in bowel habits, fever, abdominal distention, obstipation, or constipation.

For Grade 1 events, consider temporary withholding of treatment to confirm toxicity does not exceed Grade 1. Withhold study treatment for Grade 2 or 3 immune-related colitis. For moderate

(Grade 2) colitis administer corticosteroids, unless diarrhea is transient, starting with initial dose of 1 mg/kg per day prednisone or equivalent. Gastroenterology should be consulted and should consider permanent discontinuation of ipilimumab. For severe (Grade 3) or life-threatening (Grade 4) colitis, administer corticosteroids at a dose of 1 to 2 mg/kg per day prednisone equivalents (for Grade 3) or 1.0 to 2 mg/kg per day methylprednisolone equivalents (for Grade 4) followed by corticosteroid taper. If Grade 3 symptoms persist for ≥ 3 to 5 days or recur after improvement, consider administering IV corticosteroid or noncorticosteroid (eg, infliximab). Consider colonoscopy/GI endoscopy in cases where subjects have been on immunosuppression and may be at risk for opportunistic infections as an independent cause for diarrhea (ie, CMV colitis) and for those who are anti-TNF or corticosteroid refractory. When symptoms improve to \leq Grade 1, taper corticosteroids over at least 4 to 6 weeks before resuming treatment, although resuming treatment while on low-dose corticosteroid may also be an option after an evaluation of the risks and benefits. Permanently discontinue treatment for Grade 4 or recurrent colitis upon restarting study treatment.

